11.4.2 Non-Serious Adverse Event Reporting

Non-serious adverse events will be reported to the DF/HCC Overall Principal Investigator on the toxicity Case Report Forms.

11.5 Reporting to the Institutional Review Board (IRB)

Investigative sites within DF/HCC will report all serious adverse events directly to the DFCI Office for Human Research Studies (OHRs).

Other investigative sites should report serious adverse events to their respective IRB according to the local IRB's policies and procedures in reporting adverse events. A copy of the submitted institutional SAE form should be forwarded to:

The DF/HCC Principal Investigator will submit SAE reports from outside institutions to the DFCI Office for Human Research Studies (OHRs) according to DFCI IRB policies and procedures in reporting adverse events.

11.6 Reporting to Prometheus

A copy of any SAE report submitted to the DFCI IRB or FDA must be sent to Prometheus Laboratories. If the Interleukin-2 is a suspect or co-suspect drug reported on the FDA Form 3500A MedWatch report, Prometheus Laboratories also requests a courtesy copy of the FDA Form 3500A MedWatch report that was submitted to the US Food and Drug Administration, via email or fax, to Drug Safety and Pharmacovigilance at Prometheus Laboratories, Inc. Please also include your contact information.

CONFIDENTIAL

This document is confidential. Do not disclose or use except as authorized.

11.7 Reporting to Hospital Risk Management

Participating investigators will report to their local Risk Management office any subject safety reports or sentinel events that require reporting according to 'institutional policy.'

11.8 Monitoring of Adverse Events and Period of Observation

All adverse events, both serious and non-serious, and deaths that are encountered from initiation of study intervention, throughout the study, and within 30 days of the last study intervention should be followed to their resolution, or until the participating investigator assesses them as stable, or the participating investigator determines the event to be irreversible, or the participant is lost to follow-up. The presence and resolution of AEs and SAEs (with dates) should be documented on the appropriate case report form and recorded in the participant's medical record to facilitate source data verification.

For some SAEs, the study sponsor or designee may follow-up by telephone, fax, and/or monitoring visit to obtain additional case details deemed necessary to appropriately evaluate the SAE report (e.g., hospital discharge summary, consultant report, or autopsy report).

Participants should be instructed to report any serious post-study event(s) that might reasonably be related to participation in this study. Participating investigators should notify the DF/HCC Overall Principal Investigator and their respective IRB of any unanticipated death or adverse event occurring after a participant has discontinued or terminated study participation that may reasonably be related to the study.

CONFIDENTIAL

This document is confidential. Do not disclose or use except as authorized.

12. DATA AND SAFETY MONITORING

12.1 Data Reporting

12.1.1 Method

The QACT will collect, manage, and monitor data for this study.

12.1.2 Data Submission

The schedule for completion and submission of case report forms (paper or electronic) to the QACT is as follows:

Form	Submission Timeline
Eligibility Checklist	Complete prior to registration with QACT
On Study Form	Within 14 days of registration
Baseline Assessment Form	Within 14 days of registration
Treatment Form	Within 10 days of the last day of the cycle
Adverse Event Report Form	Within 10 days of the last day of the cycle
Response Assessment Form	Within 10 days of the completion of the cycle required for response evaluation
Off Treatment/Off Study Form	Within 14 days of completing treatment or being taken off study for any reason
Follow up/Survival Form	Within 14 days of the protocol defined follow up visit date or call

12.2 Safety Meetings

The DF/HCC Data and Safety Monitoring Committee (DSMC) will review and monitor toxicity and accrual data from this trial. The committee is composed of clinical specialists with experience in oncology and who have no direct relationship with the

CONFIDENTIAL

This document is confidential. Do not disclose or use except as authorized.

study. Information that raises any questions about participant safety will be addressed with the Principal Investigator and study team.

The DSMC will meet regularly to review toxicity and accrual data. Information to be provided to the committee may include: up-to-date participant accrual; current dose level information; DLT information; all grade 2 or higher unexpected adverse events that have been reported; summary of all deaths occurring within 30 days for Phase I or II protocols; for gene transfer protocols, summary of all deaths while being treated and during active follow-up; any response information; audit results, and a summary provided by the study team. Other information (e.g. scans, laboratory values) will be provided upon request.

12.3 Monitoring

Involvement in this study as a participating investigator implies acceptance of potential audits or inspections, including source data verification, by representatives designated by the DF/HCC Overall Principal Investigator (or Protocol Chair) or DF/HCC. The purpose of these audits or inspections is to examine study-related activities and documents to determine whether these activities were conducted and data were recorded, analyzed, and accurately reported in accordance with the protocol, institutional policy, and any applicable regulatory requirements.

All data will be monitored for timeliness of submission, completeness, and adherence to protocol requirements. Monitoring will begin at the time of participant registration and will continue during protocol performance and completion.

CONFIDENTIAL

This document is confidential. Do not disclose or use except as authorized.

13. REGULATORY CONSIDERATIONS

13.1 Protocol Review and Amendments

This protocol, the proposed informed consent and all forms of participant information related to the study (e.g., advertisements used to recruit participants) and any other necessary documents must be submitted, reviewed and approved by a properly constituted IRB governing each study location.

Any changes made to the protocol must be submitted as amendments and must be approved by the IRB prior to implementation. Any changes in study conduct must be reported to the IRB. The DF/HCC Overall Principal Investigator (or Protocol Chair) will disseminate protocol amendment information to all participating investigators.

All decisions of the IRB concerning the conduct of the study must be made in writing.

13.2 Informed Consent

All participants must be provided a consent form describing this study and providing sufficient information for participants to make an informed decision about their participation in this study. The formal consent of a participant, using the IRB approved consent form, must be obtained before the participant is involved in any study-related procedure. The consent form must be signed and dated by the participant or the participant's legally authorized representative, and by the person obtaining the consent. The participant must be given a copy of the signed and dated consent document. The original signed copy of the consent document must be retained in the medical record or research file.

13.3 Ethics

This study is to be conducted according to the following considerations, which represent good and sound research practice:

- US Code of Federal Regulations (CFR) governing clinical study conduct and ethical principles that have their origin in the Declaration of Helsinki
 - Title 21 Part 50 – Protection of Human Subjects
www.access.gpo.gov/nara/cfr/waisidx_02/21cfr50_02.html

CONFIDENTIAL

This document is confidential. Do not disclose or use except as authorized.

Phase II ECP and IL-2 for chronic GVHD

Version 2.0; August 15, 2016

- Title 21 Part 54 – Financial Disclosure by Clinical Investigators
www.access.gpo.gov/nara/cfr/waisidx_02/21cfr54_02.html
- Title 21 Part 56 – Institutional Review Boards
www.access.gpo.gov/nara/cfr/waisidx_02/21cfr56_02.html
- Title 21 Part 312 – Investigational New Drug Application
www.access.gpo.gov/nara/cfr/waisidx_02/21cfr312_02.html
- State laws
- DF/HCC research policies and procedures
<http://www.dfhcc.harvard.edu/clinical-research-support/clinical-research-unit-cru/policies-and-procedures/>

It is understood that deviations from the protocol should be avoided, except when necessary to eliminate an immediate hazard to a research participant. In such case, the deviation must be reported to the IRB according to the local reporting policy.

13.4 Study Documentation

The investigator must prepare and maintain adequate and accurate case histories designed to record all observations and other data pertinent to the study for each research participant. This information enables the study to be fully documented and the study data to be subsequently verified.

Original source documents supporting entries in the case report forms include but are not limited to hospital records, clinical charts, laboratory and pharmacy records, recorded data from automated instruments, microfiches, photographic negatives, microfilm or magnetic media, and/or x-rays.

13.5 Records Retention

All study-related documents must be retained for the maximum period required by applicable federal regulations and guidelines or institutional policies.

13.6 Multi-center Guidelines

N/A

13.7 Cooperative Research and Development Agreement (CRADA)/Clinical Trials Agreement (CTA)

CONFIDENTIAL

This document is confidential. Do not disclose or use except as authorized.

Phase II ECP and IL-2 for chronic GVHD

Version 2.0; August 15, 2016

N/A.

CONFIDENTIAL

This document is confidential. Do not disclose or use except as authorized.

14. STATISTICAL CONSIDERATIONS

14.1 Study Design/Endpoints

This is a one-stage Phase II trial to assess the efficacy of 16 weeks extracorporeal photopheresis (ECP) with the addition of daily low-dose subcutaneous (SC) interleukin-2 (IL-2) for weeks 8-16 in patients with steroid-refractory chronic graft-versus-host disease (cGVHD). The primary endpoint is overall response as defined in Section 10.0. Response will be evaluated at 16 weeks of treatment.

Our previous studies of low-dose IL-2 alone (DFCI#07-083, 11-149) for steroid refractory cGVHD showed a overall response rate of ~50-60%, and a randomized phase 2 trial of ECP vs. placebo showed a 40% response rate of skin cGVHD and 33% response rate of non-skin cGVHD⁴³. Conservatively extrapolating this information, we would consider ECP+IL-2 potentially efficacious if the overall response rate is 75% or higher and unworthy if 50% or lower. With 25 evaluable patients, if 17 or more patients respond, the treatment will be considered efficacious for the treatment of steroid refractory cGVHD.

With this design, the probability of concluding the treatment efficacious is 0.85 if the true but unknown response rate is 75% and 0.05 if the true rate is 50%. This decision rule is calculated using the exact binomial method. Table 1 below presents the operating characteristics of this design. Patients will be considered evaluable for response if they receive at least one week of ECP, which we anticipate to occur to all patients based on our prior experience. Patient will be replaced if the patient is removed from the study for reasons unrelated to the treatment (see Section 5.4).

Table 1. Operating Characteristics

	True but Unknown Response Rate						
	50%	55%	60%	65%	70%	75%	
Prob(≥ 17 responses in 25)	0.05	0.13	0.27	0.47	0.68	0.85	

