2.2.1.4 Clinical Experience

In DFCI 07-083, we assessed safety of low-dose interleukin-2 in participants with refractory active cGVHD. ⁴¹ The primary objective was to determine the MTD and toxicity of an 8-week course of low-dose IL-2 in chronic GVHD participants with an inadequate response to steroids. Eligibility included cGVHD that had not responded to at least 0.25 mg/kg prednisone for a 4 week period, the absence of infection, and stable doses of immune suppression for 4 weeks prior. The study had a Phase 1 dose escalation design with 3 dose levels ($0.3-, 1-, 3-; \times 10^6$ IU/m²/day for 8 weeks).

29 participants accrued: 28 evaluable for toxicity; 23 for response. IL-2 at 1×10^6 IU/m²/day was determined to be MTD. Two participants developed dose-limiting-toxicity (thrombotic microangiopathy). None experienced GVHD flare. There was no malignant disease relapse. 12 of 23 participants had objective clinical responses. Low-dose IL-2 selectively increased Treg counts in-vivo (Figure 1) without impacting conventional CD4+ T (Tcon) counts. The Treg:Tcon ratio also rose (Figure 2). NK cell counts rose to a lesser extent. Low-dose IL-2 did not impact CD8+ T, B, or NKT counts. Treg count and Treg:Tcon ratio remained elevated at 8 weeks of IL-

CONFIDENTIAL

This document is confidential. Do not disclose or use except as authorized.

Phase II ECP and IL-2 for chronic GVHD

Version 2.0; August 15, 2016

2, then declined off IL-2. IL-2-induced Treg expressed FoxP3+ and were functional in Tcon suppression assays. Importantly, clinical and immunologic responses were sustained in responders on extended-duration IL-2 therapy beyond 12 weeks, enabling a taper of concomitant immunosuppression.

Figure 1 (below left). Expansion of CD4 Treg during treatment with daily low-dose IL-2. Gating on CD3+CD4+ T, Treg are defined as CD25+CD127- (black) and Tcon are CD25-CD127+ (blue). The %Treg within the CD4 gate is indicated in each plot. Figure 1 depicts a representative patient on Dose Level B.

[figure not shown]

Figure 1

[figure not shown]

Figure 2

Figure 2 (above right): Median Treg:Tcon ratio on IL-2 therapy. There was a rapid rise and sustained plateau within a few weeks of starting IL-2, and a decline after stopping IL-2. Medians with inter-quartile range are shown.

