6.1.1 Adverse Event List for IL-2

IL-2 (Proleukin) is a commercial agent. The relevant side effects of low-dose IL-2 in HSCT patients are described below. Additional detailed toxicity information may be found in the Proleukin package insert that relates primarily to high-dose IL-2.

- Local Reaction

CONFIDENTIAL

This document is confidential. Do not disclose or use except as authorized.

Phase II ECP and IL-2 for chronic GVHD

Version 2.0; August 15, 2016

Most patients receiving daily SC low-dose IL-2 reported injection site reactions, typically focal erythema that resolved in a few days; and induration that resolved after 2-3 weeks. Dose interruptions were occasionally required in patients with more marked induration (CTC grade 3). Lengthy dose interruptions may result in patients being unevaluable for response (Section 6.2)

- Constitutional symptoms

In the HSCT setting, some patients on low-dose IL-2 developed fever, nausea and arthralgia within 72 hours of starting IL-2. Interruption of therapy resulted in symptom resolution with 3 days. Patients tolerated re-introduction of IL-2 at lower dose, with subsequent escalation to MTD dose.

- Thyroid dysfunction

Thyroid function test abnormalities were noted in some HSCT patients on low-dose IL-2. Only one patient however developed clinical hypothyroidism necessitating therapy while on IL-2. After cessation of IL-2, thyroid function returned to normal. Hence, a thyroid panel (TSH, T4, free T4) levels will be checked at study entry and week 12 while on study. Patients with evidence for hypothyroidism will be worked up (antimicrosomal, antithyroglobulin antibodies) and given replacement thyroxine as clinically indicated.

- Hematopoiesis

Early post-HSCT, low-dose IL-2 caused an initial decrease in the absolute lymphocyte count in most patients after 1 week of therapy. Thereafter, with continued infusion, a steady increase in lymphocyte count occurred in all patients. Low dose IL-2 also caused an initial increase in eosinophil counts (peak at 3 weeks) followed by a gradual decline. No changes in monocyte or neutrophil counts were observed.

The platelet count decreased by >20% in some HSCT patients on low-dose IL-2. This decrease was noted within the first 2 weeks on IL-2, and continued treatment was not associated with further declines in platelet count. No patients had >40% decline in platelet counts, and none required platelet transfusions or had bleeding episodes.

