10. MEASUREMENT OF EFFECT

Evaluable for toxicity- Participants who receive at least one dose of IL-2 will be evaluable for toxicity of IL-2 treatment.

Evaluable for response- Participants who have received at least 4 weeks of ECP+IL-2 and have had their disease re-assessed will be considered evaluable for combination ECP+IL-2 response. These participants will have their response classified according to the definitions stated below

10.1 cGVHD Assessments

Patients will undergo standardized cGVHD assessment per NIH guidelines (e.g., http://asbmt.affiniscape.com/associations/11741/files/ResponseCriteriaAPPENDIXAFor_mA.pdf) at baseline and week 8 and 16 on study.⁴⁶ cGVHD response will be assessed per NIH consensus criteria.⁴⁷ Of note, oral and ocular sites will not be included in determination of response, as additional topical therapy is permitted for those sites.

10.1.1 Complete response is defined as- Organ response: resolution of all reversible manifestations related to cGVHD in a specific organ; Overall response: resolution of all reversible manifestations in each organ or site of cGVHD involvement. Depending on relevant organ system involvement, patients will undergo repeat detailed assessment of ocular, oral, cutaneous, musculoskeletal and pulmonary systems.

10.1.2 Partial response is defined as- Organ response: at least 50% improvement in the scale used to measure disease manifestations related to cGVHD (e.g. a 50% decrease in skin rash from 80% BSA to 40% BSA), with a minimum of 25% improvement in the full scale as opposed solely to a percentage of the starting value (Appendix F; Section 17.6); Overall response: improvement in measure at least one organ or site, without progression in measures at any other organ or site. Of note, for global ratings and categorical scales, a 1-point change in a 3- or 7- point scale or a 2- to 3- change on a 0- to 10- point scale (0.5 SD change) would be considered clinically meaningful. Additionally, the hallmark for response to therapy for bronchiolitis obliterans syndrome (BOS) is stabilization of lung function with no further decrease in FEV1 during a 3-month period.

10.1.3 Non-responders (e.g., minor response, stable disease) will not have changes in cGVHD meeting NIH criteria for partial response or disease progression.

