11.1.4 Attribution

Attribution is the relationship between an adverse event or serious adverse event and the study treatment. Attribution will be assigned as follows:

- Definite – The AE is clearly related to the study treatment.

CONFIDENTIAL

This document is confidential. Do not disclose or use except as authorized.

- Probable – The AE is likely related to the study treatment.
- Possible – The AE may be related to the study treatment.
- Unlikely - The AE is doubtfully related to the study treatment.
- Unrelated - The AE is clearly NOT related to the study treatment.

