14.2 Sample Size/Accrual Rate

14.2.1 Sample Size

CONFIDENTIAL

This document is confidential. Do not disclose or use except as authorized.

Phase II ECP and IL-2 for chronic GVHD
Version 2.0; August 15, 2016

The target accrual is 25 evaluable patients.

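### Sections 14.1 and 10 define 'evaluable for response' differently, and nothing says which rule fixes the 25 patients in the 17-of-25 decision rule

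*Combined protocol and SAP*

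**What the plan says.** Section 14.1 takes overall response from Section 10 as the primary endpoint, evaluates it at 16 weeks, and declares efficacy with 17 or more responders among 25 evaluable patients. It then defines evaluability: "Patients will be considered evaluable for response if they receive at least one week of ECP". Section 14.2.1 adds only: "The target accrual is 25 evaluable patients".

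Section 10 has its own rule: "Participants who have received at least 4 weeks of ECP+IL-2 and have had their disease re-assessed will be considered evaluable" for response to the combination. It goes on to say that these are the participants whose response will be classified.

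Two other sentences bear on who is counted:

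- Section 6.1.1, on local reactions: "Lengthy dose interruptions may result in patients being unevaluable for response (Section 6.2". The section it points to, 6.2, contains no evaluability rule.
- Section 14.1, on replacement: "Patient will be replaced if the patient is removed from the study for reasons unrelated to the treatment". It refers to Section 5.4, which lists reasons for stopping without sorting them into related and unrelated.

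**The concern.** The two rules differ in agent, in length of exposure and in whether a re-assessment is needed. IL-2 normally starts after week 8, so 4 weeks of the combination is reached at about week 12. Scheduled cGVHD assessments fall at weeks 8 and 16, so on the planned schedule the first one that can reflect the combination is week 16. A patient who stops anywhere between week 1 of ECP and that point counts under 14.1 and is left out under Section 10.

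Early leavers are unlikely to be a random sample: worsening cGVHD, toxicity and malignant relapse are all reasons in Section 5.4. The trial is single-arm, with no blinding described, so the choice of rule could be made after outcomes are known. At stake is the denominator of the trial's only formal efficacy decision.

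**Working it through.** **1. The plan's own figures.** Inputs from Section 14.1: n = 25, success if X ≥ 17, rates 50% and 75%, exact binomial. P(X ≥ 17) at 50/55/60/65/70/75% is 0.0539/0.1340/0.2735/0.4668/0.6769/0.8506. All six agree with Table 1 at two decimals.

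**2. Do the texts settle the denominator?**

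| Question | Section 14.1 | Section 10 |
|---|---|---|
| Exposure needed | 1 week of ECP | 4 weeks of ECP+IL-2 |
| Re-assessment needed | not mentioned | yes |
| Tied to the 25 and the 17 | same section | only through 14.1's citation for the endpoint |
| Whose response is classified | not stated | its own evaluable set |

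The Section 6.1.1 sentence fits only a rule based on IL-2 exposure. Under one week of ECP, an IL-2 interruption cannot make a patient unevaluable. Replacement does not settle the matter either. The scale in Section 11.1.4 ("Attribution is the relationship between an adverse event or serious adverse event and the study treatment") helps for adverse events. It does not classify malignant relapse as a reason for removal. Life-threatening infection is a 5.4 reason, while 6.2 declares infection not IL-2 related.

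**3. What the choice can do.** Let d be the share with at least one week of ECP who never meet Section 10. The documents give no d for this trial, so 5% and 10% are assumptions, as is that none of the lost respond.

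*Case A. 50% is the rate over all treated patients, and the Section 10 set is filled to 25.* The top-up is also an assumption, inferred from the target in 14.2.1. The rate among those kept is 0.50/(1 − d):

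- d = 5%: 0.50/0.95 = 0.526, so P(X ≥ 17) = 0.089
- d = 10%: 0.50/0.90 = 0.556, so P(X ≥ 17) = 0.146

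*Case B. 75% is the rate in the Section 10 set, and the 14.1 set of 25 is analysed with losses as failures.* The rate is 0.75 × (1 − d):

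- d = 5%: 0.7125, so power = 0.726
- d = 10%: 0.675, so power = 0.573

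**4. Sensitivity to the assumptions.**

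- In case A, if a quarter of the lost would have responded, the rate among those kept is (0.50 − 0.25d)/(1 − d), and the false-positive probability is 0.070 or 0.092. If half would have responded, it stays at 0.054.
- In case B, if 50% also describes the Section 10 set, the rate 0.50 × (1 − d) gives a false-positive probability of 0.03 or 0.02, below the stated level.
- With d = 0 the two sets coincide and nothing changes.

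**5. Is early loss plausible?** Section 2.2.1.4 reports for trial 07-083: "29 participants accrued: 28 evaluable for toxicity; 23 for response". So 6 of 29 (21%) were not response-evaluable. That was a dose-escalation trial of IL-2 alone, and its evaluability rule is not given. It shows that such losses occur, not how many to expect here.

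**The case against.** The strongest defence is that 14.1 governs by position: its one-week sentence stands with the 25, the 17 and Table 1, and it cites Section 10 for what a response is, not for who is counted. Section 10's set would then be a separate one for the combination. This is a workable default and supports choosing the 14.1 set in the fix. It does not remove the conflict, because the primary objective in Section 1.2 is that same combination response, and Section 10 provides for classifying response only in its own set.

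It is also fair that the sets are nested, and that the size rests on assumed losses. Three stronger readings are tempting, and the documents do not support them:

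- *The same data would readily give opposite decisions.* Suppose 16 of 25 respond under 14.1 and Section 10 drops 3 non-responders. Without a top-up the count is 16 of 22, still short of 17. A reversal needs added patients, which no sentence provides for on this ground, and a result of exactly 16 of 25 (probability 0.06 at a true 50%, 0.08 at 75%).
- *Table 1 is wrong, or the trial is too small.* The table is right for the set its rates describe. Power falls short only if 75% describes a different set from the one analysed.
- *The IL-2 benchmark is really 41%.* The plan reports that "12 of 23 participants had objective clinical responses" (52%). Dividing 12 by the 29 accrued gives 41%, but the documents do not report the outcome of the other 6.

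**Conclusion.** The concern holds: the plan has two rules for one term, no order between them, and a primary decision that depends on which is used. The contradiction is certain from the text; its numerical effect is not. At assumed losses of 5% and 10%, all non-responders, the false-positive probability is 0.09 and 0.15 (case A, with top-up) or power is 0.73 and 0.57 (case B), against stated values of 0.05 and 0.85. Other readings of what the rates describe leave the error rate unchanged or lower it. It must be fixed because the primary population should not be open to choice once responses are known.

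**What to change.** - **Section 14.1:** name the patients with at least one week of ECP as the single primary population for the 17-of-25 rule. Score by the week-16 assessment where one exists. Count a patient with no week-16 response assessment as a non-responder, unless replaced for a reason listed in advance.
- **Section 10:** relabel the set with 4 weeks of ECP+IL-2 as a sensitivity analysis, and align the Section 6.1.1 sentence with this.
- **Sections 5.4 and 14.1:** list in advance which removal reasons are unrelated to treatment and lead to replacement. Report the outcomes of replaced patients.
- **Section 5:** it says progression during taper of other immunosuppression is not evidence of lack of efficacy, while Section 5.4 makes worsening that needs a new immunosuppressive drug a removal reason. Reconcile these with how such removals are scored for the primary endpoint.
- **Rates:** state which set the 50% and 75% describe. If it is not the primary set, restate the power.

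The cost is wording only, with no new procedures. If both rates already describe the primary set, Table 1 and the 25 patients stand. The downside is that the observed response rate may be slightly lower, since early leavers without a week-16 assessment count as failures.

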5.4 Duration of Therapy

Duration of therapy will be as per the schema outlined previously. In the absence of treatment delays due to adverse events, ECP plus IL-2 treatment may continue until one of the following criteria applies:

- The subject withdraws consent
- Non-compliance
- Administrative reasons
- Unacceptable adverse event
- Life threatening anaphylactic reaction to IL-2
- Other grade 4 toxic event (unless it is an asymptomatic correctable laboratory result, e.g. uric acid)
- Recurrent or non-resolving grade 3 toxic event
- Severe hematologic toxicity that persists or recurs (section 6.2).
- Life threatening infection on IL-2, at the discretion of the treating physician.
- Malignant relapse
- Clinical worsening of GVHD requiring the addition of a new immunosuppressive medication per the judgment of the treating physician. An increase in the corticosteroid dose will be considered evidence of worsening GVHD. Changes in other immunosuppressive medication doses to maintain a therapeutic level alone will not be criteria for removal from the trial.
- General or specific changes in the participant's condition render the participant unacceptable for further treatment in the opinion of the treating investigator.

CONFIDENTIAL

This document is confidential. Do not disclose or use except as authorized.

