5.6 Criteria for Removal from Study

Participants will be removed from study when any of the criteria listed in Section 5.4 applies. The reason for study removal and the date the participant was removed must be documented in the study-specific case report form (CRF). Alternative care options will be discussed with the participant.

In the event of unusual or life-threatening complications, participating investigators must immediately notify the Principal Investigator.

[name] DPhil,

[REDACTED]
[REDACTED]

CONFIDENTIAL

This document is confidential. Do not disclose or use except as authorized.

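### The 25 patients behind the 17-of-25 rule are defined inconsistently: evaluable after one week of ECP, replaceable at any later time, and subject to a different rule in Section 10

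*Combined protocol and SAP*

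**What the plan says.** Section 14.1 sets the decision rule at 17 or more responders among 25 evaluable patients, with 50% as the unworthy rate and 75% as the target. Section 14.2.1 repeats the count: "The target accrual is 25 evaluable patients". Four places bear on who is counted.

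- **Section 14.1, evaluability:** "Patients will be considered evaluable for response if they receive at least one week of ECP". The authors expect every patient to reach this point.
- **Section 14.1, next sentence, replacement:** "Patient will be replaced if the patient is removed from the study for reasons unrelated to the treatment (see Section 5.4").
- **Section 10**, which 14.1 names as the source of the endpoint definition, describes those evaluable for combination response as "Participants who have received at least 4 weeks of ECP+IL-2 and have had their disease re-assessed".
- **Section 6.1.1**, on local reactions, warns that long dose interruptions may make a patient unevaluable and points to Section 6.2. Section 6.2 contains no evaluability rule.

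For removal itself, Section 5.6 says: "Participants will be removed from study when any of the criteria listed in Section 5.4 applies". The Section 5.4 list runs from withdrawn consent, non-compliance and administrative reasons through toxicity, malignant relapse and worsening GVHD to changes in condition that "render the participant unacceptable for further treatment in the opinion of the treating investigator". No item is labelled related or unrelated to treatment.

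**The concern.** With a fixed cut-off of 17, one or two patients can decide the result, so membership of the 25 has to be settled before outcomes are known. Here it is not. A patient removed at week 10 for a reason judged unrelated to treatment is evaluable under one sentence of 14.1 and replaced under the next. If IL-2 started on schedule, that patient is also not evaluable under Section 10.

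The trial is single-arm, and no one is named to decide whether a removal was unrelated. That decision could be made case by case with the patient's course already known. If the patients who drop out of the count respond less often than those who stay, the observed rate moves up and the error rate in Table 1 no longer describes the rule in use.

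**Working it through.** **1. The plan's own figures.** Inputs from Section 14.1: n = 25, cut-off 17, rates 50% and 75%, exact binomial. P(X ≥ 17 | n = 25, p) for p = 0.50, 0.55, 0.60, 0.65, 0.70, 0.75 is 0.0539, 0.1340, 0.2735, 0.4668, 0.6769, 0.8506. Table 1 gives 0.05, 0.13, 0.27, 0.47, 0.68, 0.85. It reproduces throughout, so the arithmetic is sound for 25 unselected patients.

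**2. The definitions side by side.**

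| Source | Counted if | Earliest time on schedule |
|---|---|---|
| 14.1, evaluability | one week of ECP | week 1 |
| 14.1, replacement | not removed for an unrelated reason | no time limit |
| Section 10 | 4 weeks of ECP+IL-2 and re-assessed | about week 12 (IL-2 starts after week 8; 8 + 4 = 12) |

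Nothing says which rule gives the primary denominator, or how a patient without a week-16 assessment is counted. If an evaluable patient stays in and is also replaced, there are 25 + 1 = 26 evaluable patients, and the plan has no cut-off for 26.

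**3. Can the Section 5.4 reasons be sorted?** In part. Section 11.1.4 grades attribution of adverse events, ending at "Unrelated - The AE is clearly NOT related to the study treatment". Section 11.1.1 defines an adverse event broadly enough that relapse or decline arising on study can be graded in this way. Consent withdrawal, non-compliance and administrative reasons are not medical events, so the scale does not reach them.

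**4. One conditional scenario for the false-positive risk.** Assume that 50% is the rate among all patients with one week of ECP and that replaced patients leave the 25. Let q be the share replaced and r the response rate they would have had. The rate among those counted is

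p = (0.50 − q·r) / (1 − q),

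and the risk is P(X ≥ 17 | 25, p). Both q and r are assumptions.

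| q | r = 0.25: p → risk | r = 0: p → risk | r = 0.50: p → risk |
|---|---|---|---|
| 4% | 0.510 → 0.066 | 0.521 → 0.081 | 0.500 → 0.054 |
| 8% | 0.522 → 0.082 | 0.543 → 0.120 | 0.500 → 0.054 |
| 12% | 0.534 → 0.103 | 0.568 → 0.178 | 0.500 → 0.054 |

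For example, with q = 8% and r = 0.25: (0.50 − 0.02)/0.92 = 0.522. The r = 0 column is an upper bound. The r = 0.50 column is removal independent of response. If 50% instead refers to the patients who are counted, or if evaluable patients stay in the 25, the risk is 0.054 whatever q is.

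**5. What the repair costs in power.** Suppose 75% and 50% were meant only for patients not removed, and removed patients now count as non-responders. The rates become 0.75(1 − q) and 0.50(1 − q).

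| q | Target rate → power | Null rate → risk |
|---|---|---|
| 4% | 0.72 → 0.75 | 0.48 → 0.035 |
| 8% | 0.69 → 0.64 | 0.46 → 0.022 |
| 12% | 0.66 → 0.51 | 0.44 → 0.013 |

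If the two rates are meant for all patients with one week of ECP, power stays at 0.85.

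**The case against.** The sentences can be read so that they agree. Replacement may have been meant only before one week of ECP, and Section 10, which speaks of combination response, may describe a separate set. Neither is stated. The first reading would also leave the replacement rule almost nothing to do, since 14.1 expects every patient to reach one week.

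The stronger objection is to the size. Inflation needs three things together: 50% applies to all patients with one week of ECP, replaced patients leave the 25, and they respond less often. The documents lean against the first. In the earlier IL-2 trial (07-083), one source of the benchmark, Section 2.2.1.4 reports "29 participants accrued: 28 evaluable for toxicity; 23 for response", and the only response count given is 12 of those 23. That suggests a rate among evaluable patients, although that trial's evaluability rule is not given. The upper bounds are also severe. Toxicity judged related to treatment is not replaceable, worsening GVHD is naturally an outcome of treatment, and a patient who withdraws for other reasons is not a certain non-responder. All of this stands, which is why the figures are one scenario and not an estimate.

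A reader might take the 6 of 29 not evaluable in 07-083 (21%) as the likely share replaced here, or recompute that trial's rate as 12/29 = 41%. The documents support neither. The reasons for non-evaluability are not given, and the benchmark also draws on a second IL-2 trial and a randomized ECP trial.

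**Conclusion.** The inconsistency is in the text and affects the primary decision, so it should be fixed. The sample-size arithmetic is not at fault. Under the scenario in step 4 of the working, the false-positive risk is 0.066 to 0.103 for 4 to 12% replaced, with upper bounds of 0.081 to 0.178, against 0.054 for unselected patients. These shares and response rates are assumed, because the documents give no removal rate. I put no separate figure on the Section 10 difference, because the documents do not say how many patients will fall short of 4 weeks of ECP+IL-2.

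A reader might infer that the trial's error rate is in fact inflated, or that the Section 5.4 reasons cannot be sorted at all. Neither follows. The risk stays at 0.054 under any of three readings or conditions that the plan leaves open, and the attribution scale handles the medical events. What is established is that the plan does not say which reading applies.

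**What to change.** In Section 14.1, state that:

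- the primary analysis set is the first 25 patients who receive at least one week of ECP;
- only patients who do not reach that point are replaced;
- all others stay in the denominator whatever the reason for removal;
- patients without CR or PR at week 16, including those not assessed, count as non-responders;
- the 50% and 75% rates refer to this set.

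In Section 10, label the set with 4 weeks of ECP+IL-2 plus re-assessment as a secondary, sensitivity analysis.

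The cost is a few sentences. If the two rates are meant for this set, the 25 patients, the cut-off of 17 and the power of 0.85 are unchanged. The observed response rate may be less favourable. If the authors meant 75% only for patients not removed, power falls as in step 5 of the working, and the stated power should be restated.
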